  - i. 4(a) To assess the acceptability and feasibility of PoC syphilis testing and treatment. (Dual HIV and syphilis PoC testing will be offered to pregnant women who are HIV uninfected/undiagnosed and rapid syphilis testing for pregnant women with a known HIV infection). Our primary outcome will be defined as acceptability of testing, which is the proportion of women tested out of all those eligible and seeking care in the study clinics. Secondarily, we will assess the proportion of women who received treatment among those with a reactive syphilis test result. We will assess any treatment, treatment completion, and time to treatment.
  - ii. To evaluate the unit costs and patient costs associated with antenatal PoC syphilis testing and treatment compared to the standard of care the standard of care.

Flow diagram

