**Outcomes:** Our primary outcome is acceptability of syphilis testing at the first ANC visit (proportion tested for syphilis out of all eligible women receiving care in the study clinics during implementation of the study). For participants in the PoC clinic, acceptability will be defined as having a PoC test with recorded results. Those who decline PoC testing will be identified as not accepting and will be included in the denominator. For those in the standard of care, the numerator will be women who receive an RPR/VDRL syphilis test recorded in patient-held or clinic records. The denominator for both groups will be all women attending the study clinic during implementation and eligible for participation (1. Age  $\geq$  15 years, 2. Currently pregnant, 3. Attending first ANC visit, 4. 27 weeks of gestation or less, 5. Will reside

Title: The diagnosis and treatment of *Chlamydia trachomatis* and *Neisseria gonorrhoeae* in pregnant women to prevent adverse neonatal consequences.”

in Gaborone through the time of delivery and 1st postnatal visit, And 6. Mentally competent to understand the informed consent).

Additional outcomes will be related to treatment and costs. We will report the proportion of women who received treatment among those with a reactive syphilis test result. We will assess differences in any treatment, treatment completion, and time to treatment.

The primary cost outcome is the average unit cost per woman tested for each strategy and will include both patient-related costs and healthcare system costs. Healthcare-related cost data will be collected from in-country data sources. Patient data will be collected from the short survey.

**Analysis:** First, comparisons will be made across four groups of participant data: **1)** participants in the standard of care clinic enrolled as part of the CT/NG study prior to implementation of the syphilis testing sub-study called “Standard of Care pretest” (n=100); **2)** participants in the standard of care clinic enrolled as part of the syphilis testing sub-study called “Standard of Care post-test” (n=200); **3)** participants in the PoC clinic enrolled as part of the CT/NG study prior to implementation of the syphilis testing sub-study called “PoC pretest” (n=100); and **4)** participants in the PoC clinic enrolled as part of the syphilis testing sub-study called “PoC post-test” (n=200).

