To assess differences in receipt of syphilis testing, we will use a difference-in-difference (DiD) strategy, which takes the difference between two before and after differences (pre-post-test with comparison).[25] DiD will be performed using a logistic regression model with a variable for whether the individual was in the PoC clinic (PoC), whether or not it is the post period (Post), an interaction variable for the product of those two variables, and covariates. The primary outcome (Y) is the proportion of eligible women who are tested for syphilis at their first ANC visit:

$Y=a+bPoCPoC+bPostPost+bint(Post*PoC)+bcovariates$  Models will also be stratified by HIV status to see if PoC had a differential impact among WLH. Variables for which there were significant differences between the intervention and comparison group will be included in multivariable model.

Secondarily, will also assess receipt of treatment using DiD analysis by comparing the pre-test and post-test differences in terms of the proportions of participants who had a reactive test who: 1) received the first dose of treatment, and 2) completed treatment. Prevalence of syphilis will also be reported according to treatment group and HIV status as the proportion of individuals testing positive divided by the number of individuals tested. Exact binomial 95% confidence intervals for prevalence will be estimated. All analyses will be conducted with Stata 17.0 (Stata Corporation, College Station, TX).

To compare differences in costs, recurrent costs will be calculated per test, and capital and training costs will be summed and divided by the number of women tested. Those costs will be added to get an average unit cost for each strategy. For the intervention strategy, we will also calculate the average cost by HIV status at first ANC (i.e. the cost of delivering the dual HIV/syphilis test and the rapid syphilis). We will compare the mean costs using the non-parametric Mann-Whitney U test. For hypothesis 4, patient costs will be summed and an average patient cost will be calculated for each strategy, which will be compared using either the Mann-Whitney U test or Student's t-test. Cost components will be examined to determine key cost drivers and to identify potential efficiencies that could be achieved in future scale-up.

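### Aim 4's primary outcome counts a different test in each clinic, so the difference-in-difference mixes a change of test with a change in receipt of syphilis testing

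*Protocol*

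**What the plan says.** Protocol section 2, Aim 4(a), gives the primary outcome as acceptability of testing: "the proportion of women tested out of all those eligible and seeking care in the study clinics". Section 3, Specific Aim 4, Outcomes, then sets the numerator clinic by clinic.

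- PoC clinic: "For participants in the PoC clinic, acceptability will be defined as having a PoC test with recorded results". Also: "Those who decline PoC testing will be identified as not accepting and will be included in the denominator".
- Standard of care: "For those in the standard of care, the numerator will be women who receive an RPR/VDRL syphilis test recorded in patient-held or clinic records".
- Denominator: "The denominator for both groups will be all women attending the study clinic during implementation and eligible for participation".

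The Analysis paragraphs compare four cells: standard of care pretest (n=100) and post-test (n=200), and PoC pretest (n=100) and post-test (n=200). Both pretest cells are women "enrolled as part of the CT/NG study prior to implementation of the syphilis testing sub-study".

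The purpose and outcome of the model are stated as follows: "To assess differences in receipt of syphilis testing, we will use a difference-in-difference (DiD) strategy", and "The primary outcome (Y) is the proportion of eligible women who are tested for syphilis at their first ANC visit". It is a logistic regression with PoC, Post, their product and covariates. The model text does not say which test counts in which cell.

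Aim 4 also says that the PoC test is added to routine testing, and its Laboratory Testing paragraph keeps RPR/VDRL for all participants. The SAP contains no Aim 4 analysis, so it does not settle the matter.

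**The concern.** A DiD removes a fixed difference between clinics and a shared change over time. It cannot remove a change in the outcome definition that occurs only in the treated clinic in the later period. That is what happens if PoC pretest women are judged on RPR/VDRL and PoC post-test women on the PoC test.

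The effect on individual women is plain. A woman in the PoC clinic who declines the PoC test but has an RPR/VDRL is scored as untested. In the standard of care clinic the same woman is scored as tested.

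The Post × PoC term is Aim 4's primary contrast. It could suggest that testing fell when every woman who would have been tested still was. It could also understate a real gain.

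**Working it through.** **No planned figure to reproduce.** The documents give no power, effect size, RPR/VDRL coverage or PoC acceptance for Aim 4. Section 1 says only that syphilis testing coverage is suboptimal. All rates below are therefore assumed.

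**Which rule applies in each cell**

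- Standard of care, pretest and post-test: recorded RPR/VDRL, from Outcomes.
- PoC post-test: recorded PoC test, from Outcomes.
- PoC pretest: the PoC-clinic rule is the only one stated, but these women enrolled before the sub-study. The section 21 timeline has CT/NG enrollment starting in February 2021 and syphilis post-test enrollment starting in August 2022.

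**Notation.** c is RPR/VDRL coverage, assumed equal and unchanged in all four cells. a is PoC acceptance in the PoC post-test cell. U is the proportion in that cell with any syphilis test.

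**Reading 1, literal rule.** PoC pretest is 0/100. DiD = (a − 0) − (c − c) = a. The log-odds of 0 is minus infinity, so the logistic interaction is not finite. With a between 70% and 95%, the DiD is +70 to +95 points.

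**Reading 2, RPR/VDRL for PoC pretest.** The Aim 1 Data collection paragraph abstracts receipt of syphilis testing, so this can be built. Own-test DiD = (a − c) − (c − c) = a − c.

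**Any test in all four cells.** U lies between max(a, c) and min(1, a + c). Any-test DiD = U − c, which lies between max(0, a − c) and min(1 − c, a).

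**Gap.** (U − c) − (a − c) = U − a, which lies between max(0, c − a) and min(1 − a, c). So the own-test DiD is never above the any-test DiD and falls short by at most 1 − a.

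| c | a | Own-test DiD | Any-test DiD | Gap |
|---|---|---|---|---|
| 90% | 80% | −10 points | 0 to +10 | 10 to 20 |
| 60% | 90% | +30 points | +30 to +40 | 0 to 10 |
| 80% | 95% | +15 points | +15 to +20 | 0 to 5 |

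Over c from 60% to 95% and a from 70% to 95%, the own-test DiD runs from −25 to +35 points, the any-test DiD from 0 to +40, and the gap from 0 to 30.

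**Scale of the first row.** The ratio of odds ratios is (0.8/0.2)/(0.9/0.1) = 0.44. The unadjusted standard error of the own-test DiD is √(0.8×0.2/200 + 0.9×0.1/100 + 0.9×0.1/200 + 0.9×0.1/100) = 0.0552, so the 95% half-width is 1.96 × 0.0552 = 10.8 points. The gap of 10 to 20 points is about as large as sampling error or larger.

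**Denominator.** The stated denominator is all eligible attendees during implementation. The DiD cells are enrolled women, and the two pretest cells precede implementation.

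**The case against.** The by-clinic numerators may be deliberate. Aim 4's primary outcome is acceptability, costs are compared by strategy, and uptake of the test that each clinic offers is a coherent outcome. Under it, PoC pretest would naturally be RPR/VDRL, and the omission shrinks to one sentence. This stands as a legitimate alternative, but the Analysis text says that the model assesses receipt of syphilis testing, and own-test uptake does not answer that.

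A reader might infer that the plan names no test for any cell. That goes too far: the model refers to the primary outcome, and Outcomes supplies a rule for three cells. What is open is PoC pretest, and whether an RPR/VDRL counts for a PoC post-test woman who declines.

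A reader might also infer that the planned analysis will show a false fall in testing. The documents do not support that. The own-test form is an inferred reading, and a negative value needs acceptance below routine coverage. Enrolled women have had PoC testing explained to them, so their acceptance may be high. At a = 95% the shortfall is at most 5 points. Coverage described as suboptimal does not point to acceptance below it.

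Finally, an any-test outcome counts women who refused PoC as tested if they had an RPR/VDRL, and it saturates when routine coverage is near complete. This is true, and it is why acceptance needs its own report.

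**Conclusion.** The point holds and should be corrected. Following the stated rule gives either an empty PoC pretest cell with no finite interaction, or an outcome whose definition changes only in the PoC post-test cell. Neither measures the change in receipt of testing that the model is meant to assess.

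The results that do not depend on particular rates are these. With an add-on test and stable, equal RPR/VDRL coverage, the own-test DiD is a − c, it never exceeds the any-test DiD, the shortfall is at most 1 − a, and its sign is negative whenever a < c. The point figures are illustrations only. If acceptance exceeds coverage, the own-test figure equals the lower bound of the any-test DiD and the shortfall may be small.

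The gap between the own-test DiD and a DiD that counts RPR/VDRL alone should not be read as an error. The latter is zero only because coverage is assumed constant, and it ignores the test being introduced. The mismatch between eligible attendees and enrolled women is a lesser matter of description.

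**What to change.** 1. For the DiD, use one numerator in all four cells, including PoC pretest: any syphilis test, PoC or RPR/VDRL, done at the first ANC visit and recorded.
2. Abstract RPR/VDRL receipt and date for the 200 PoC post-test women. The Aim 4 Data collection paragraph describes this review for the standard of care clinic only.
3. Show the RPR/VDRL-only proportion in each cell descriptively, so that any change in routine testing is visible.
4. Report PoC acceptance separately, as a proportion in the PoC clinic, with decliners in the denominator.
5. Describe the DiD population as enrolled women, because the pretest cells precede implementation.

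If uptake of each clinic's own test is the intended contrast, say so, define PoC pretest as RPR/VDRL, and do not label or interpret the interaction as a change in receipt of syphilis testing.

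The cost is modest record abstraction and a few lines of Protocol text. There are two downsides. The DiD no longer measures acceptability, which item 4 covers. With an add-on test and stable RPR/VDRL coverage, the any-test DiD cannot be negative and has little room to rise if coverage is already high, which is why item 3 is needed.

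### Aim 4 defines its difference-in-difference on the proportion tested, but the only DiD term it specifies is a logistic interaction, a ratio of odds ratios that can differ in size and sometimes in sign

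*Protocol*

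**What the plan says.** All of this is in Protocol section 3, Study Design, under Specific Aim 4, Analysis.

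- DiD is defined as a method that "takes the difference between two before and after differences".
- The outcome is on the proportion scale: "The primary outcome (Y) is the proportion of eligible women who are tested for syphilis at their first ANC visit".
- The model is named: "DiD will be performed using a logistic regression model". Its terms are clinic, period, "an interaction variable for the product of those two variables, and covariates".
- The printed equation has no logit or other link: "Y=a+bPoCPoC+bPostPost+bint(Post*PoC)+bcovariates".
- The secondary treatment outcomes are also framed as proportions: "comparing the pre-test and post-test differences in terms of the proportions of participants who had a reactive test".
- The four groups are standard clinic pre-test (100) and post-test (200), and PoC clinic pre-test (100) and post-test (200).

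The text does not say which quantity will be reported as the DiD. It plans no marginal effects, contrast of predicted probabilities, or identity-link model. The SAP has no Aim 4 analysis, so it does not settle the point.

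**The concern.** The definition, the outcome and the equation point to a difference of differences in percentage points. The named model, read through its interaction term, gives something else: the odds ratio (post against pre) in the PoC clinic divided by the same odds ratio in the standard clinic. A few points near 100% are a large change in odds, while the same points near 60% are a small one. If the clinics start at different coverage, equal gains in points are therefore unequal gains in odds.

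The clinics are designated, not randomised, so equal pre-test coverage cannot be presumed. The primary Aim 4 outcome is testing coverage. If the interaction were reported as the DiD, PoC testing could appear to raise coverage more than usual care when, in points, coverage rose by the same amount or less.

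**Working it through.** **Inputs.** Group sizes come from the protocol: 100, 200, 100, 200. It gives no coverage rate, expected effect or power for Aim 4 (section 1 says only that coverage is suboptimal), so there is no stated figure to reproduce. Every rate below is an assumption. The calculations are unadjusted and treat women as independent.

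**Formulas.** Let s0, s1 be standard clinic pre and post, and p0, p1 PoC clinic pre and post.

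- Additive DiD = (p1 - p0) - (s1 - s0). Its variance is the sum over cells of rate × (1 - rate)/n.
- Ratio of odds ratios (ROR) = [odds(p1)/odds(p0)] / [odds(s1)/odds(s0)]. The variance of log ROR is the sum over cells of 1/[n × rate × (1 - rate)].

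**Case A: standard 50% to 70%, PoC 80% to 97%.**

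- DiD = 0.17 - 0.20 = -0.03.
- SE = √(0.00250 + 0.00105 + 0.00160 + 0.00015) = 0.0728. The 95% CI is -17.3 to +11.3 points.
- ROR = (32.33/4.00)/(2.333/1.00) = 8.083/2.333 = 3.46.
- SE of log ROR = √(0.0400 + 0.0238 + 0.0625 + 0.1718) = 0.546. The 95% CI is 1.19 to 10.10, p = 0.023.

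**Case B: standard 70% to 80%, PoC 88% to 95%.**

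- DiD = 0.07 - 0.10 = -0.03, SE 0.0648, 95% CI -15.7 to +9.7 points.
- ROR = (19/7.333)/(4/2.333) = 2.591/1.714 = 1.51, 95% CI 0.54 to 4.25, p = 0.43.

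**Case C: standard 80% to 85%, PoC 90% to 95%.** DiD = 0; ROR = 2.111/1.417 = 1.49, 95% CI 0.49 to 4.50, p = 0.48.

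**Case D, the other direction: standard 85% to 95%, PoC 70% to 82%.** DiD = +2 points; ROR = 0.58 (0.21 to 1.60).

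**When the signs agree.** With equal pre-test rates (80% to 85% against 80% to 95%), or no change in the standard clinic (70% to 70% against 85% to 95%), DiD is +10 points and ROR is 3.35 in both.

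**How often signs differ.** On a grid of all four rates from 50% to 98% in 2-point steps, 18,636 of 380,108 combinations with both measures non-zero (4.9%) had opposite signs. Every one had unequal pre-test rates and both clinics moving in the same direction. This is a share of an arbitrary grid, not a probability for this study.

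**Error rate when the additive DiD is truly zero.** Simulation used 200,000 data sets per scenario, a two-sided 5% Wald test, and 0.5 added to each count for the logit:

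| Standard | PoC | Logistic interaction rejects | Additive test rejects |
|---|---|---|---|
| 80% to 85% | 90% to 95% | 10% | 5% |
| 70% to 80% | 85% to 95% | 24% | 5% |
| 60% to 75% | 80% to 95% | 42% | 5% |

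**Cells at 100%.** If every woman in a cell is tested, that cell's odds are infinite and the interaction has no finite ordinary maximum-likelihood estimate. The planned stratification by HIV status makes cells smaller and this more likely.

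**Treatment outcomes.** Section 7, Treatment, puts syphilis prevalence below 5%. That implies fewer than 0.05 × 100 = 5 reactive women per pre-test cell and fewer than 0.05 × 200 = 10 per post-test cell. If, as an assumption, 95% of 9 reactive women were treated, all 9 would be treated with probability 0.95^9 = 63%.

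**The case against.** The strongest reply is that the plan nowhere says the odds-ratio ratio is the effect to be reported. A logistic model with this interaction can yield a double difference of predicted probabilities in the software the protocol names, and the printed equation may be shorthand for the linear predictor. This stands. A reader might infer that the plan commits to the wrong estimator, or that the printed equation commits it to a linear probability model. The documents support neither. They leave the reported scale unstated.

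Second, the reversal rests on assumed rates and needs two conditions together. In cases B to D neither measure is significant, so none of them would lead to a claim of benefit. Case A would, but it takes a 30-point baseline gap and a 20-point rise in the clinic without PoC testing. This also stands: the documents do not show that a reversal is likely. The difference in size, however, does not depend on a reversal.

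Third, neither scale is uniquely right for DiD, since parallel trends in points are no more assured than in log-odds near a ceiling. True, but it does not answer the mismatch: the plan chose proportions in its own definition.

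Fourth, a 100% cell does not make estimation impossible, because penalised or exact methods remain. Women who decline PoC testing stay in the denominator, which makes 100% less likely in that cell. A linear model has its own boundary problem, since a 100% cell adds no estimated variance and the interval becomes too narrow. All of this is accepted.

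**Conclusion.** The concern holds as a mismatch between the DiD that the plan defines and the only DiD term that it specifies. Under assumed rates at the planned group sizes, the two can disagree enough to change the conclusion: -3 points with a CI spanning zero, against a ratio of 3.46 with p = 0.023. Less extreme rates give disagreement in sign without significance on either scale. A sign change requires unequal pre-test coverage and same-direction movement in both clinics.

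It would go too far to say that the analysis will favour PoC testing wrongly, that logistic regression is unsuitable, or that the interaction could not be estimated by any method. The protocol gives no coverage rates and does not name the quantity to be reported. The change should be made because it concerns the primary Aim 4 outcome and costs little.

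**What to change.** 1. State that the primary Aim 4 estimate is the DiD in percentage points with a 95% CI. Obtain it as the double difference of predicted probabilities from the planned logistic model (delta-method or bootstrap CI), or from an identity-link or linear probability model with robust standard errors. Without covariates these give the same point estimate; with covariates they can differ, so name one.
2. If the logistic route is kept, specify the double difference itself. The contrast that only sets the interaction to zero in the PoC post-test cell keeps the sign of the interaction. In case A it compares 97% with 9.333/10.333 = 90.3% and gives +6.7 points, not -3.
3. Report the odds-ratio ratio as secondary, and correct the printed equation to match the model used. If the ratio is in fact the intended estimand, reword the DiD definition instead.
4. State how intervals will be formed if a cell is at or near 100%.
5. For the two treatment outcomes, report proportions with exact intervals descriptively. With fewer than about 5 to 10 reactive women per cell, neither regression should be relied on.

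The cost is a few sentences in the analysis section and one extra post-estimation step. No new data are needed. The downside is the care needed with intervals near 100%.

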**Laboratory Testing :** Once the specimen is collected, study staff will follow instructions for sample preparation and testing. Luminex assays enable fast and accurate cytokine measurements by utilizing specially prepared microspheres, internally dyed with a graded mixture of red or infrared fluorescent dyes. Varying the degree to which the beads are internally dyed creates hundreds of different fluorescent profiles that can be individually interrogated and classified in a single sample. The BHP lab in Gaborone can conduct cytokine analysis using an ELISA quantitative; however, this assay is currently limited to only IL-6, ICAM1, and VCAM. Further, the ELISA is a single assay and sample processing would be costly and time-consuming compared to the Luminex multiplex assay.

**Specific Aim 4:** To determine the acceptability, feasibility, and costs of implementing point-of-care (PoC) syphilis testing and treatment among pregnant women in Botswana by offering: 1) dual HIV and syphilis PoC testing for pregnant women who are HIV uninfected/undiagnosed and 2) PoC syphilis testing for pregnant women with a known HIV infection with same-day treatment to women in the designated PoC clinic. PoC testing will be offered in addition to routine syphilis and HIV testing.

**Methods and Procedures:** An additional 200 antenatal patients at the designated PoC clinic and 200 at the ‘standard of care’ clinic will be enrolled (400 total). In the PoC clinics, participants who are HIV uninfected/ undiagnosed will be offered PoC dual HIV/syphilis testing and women living with HIV will be offered a PoC syphilis test. PoC participants will receive same-day results and treatment. Participants in the standard of care clinic will continue to receive the usual care.

Additionally, analysis will incorporate the data from 200 participants previously enrolled in the CT/NG parent study. These data will be used as a “pre-test” and will include all 100 women enrolled in the standard of care clinic and all 100 women enrolled in the PoC testing clinic.

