## 5. Characteristics of the Subject Population:

### a. Number of subjects / Sample size:

Pregnant women attending their first ANC care visit at 27 weeks gestation or less. Participants must be 15 years of age and not treated with azithromycin, doxycycline, cefixime, or ceftriaxone in the past 30 days.

**Specific Aim 1 (STI testing group):** We will recruit 250 study participants for CT and NG testing.

**Specific Aim 2 (Standard of care comparison group):** We will recruit 250 antenatal patients from designated study ‘standard of care’ clinics who will be enrolled as a comparison group receiving the standard care with additional IPV and partner services and postnatal care testing (Total N=500). Among participants who test positive during postnatal care, we will offer infant testing (Estimated N=30 infants).

For Specific Aims 1 & 2, study staff will remain at study clinics during operating hours for the duration of the recruitment period. We will consecutively screen all pregnant women for eligibility and offer enrollment to all eligible women.

**Specific Aim 3 (Inflammatory markers):** We will include women in the STI testing group (Estimated N=250).

**Specific Aim 4:** We will enroll an additional 400 antenatal patients for the PoC syphilis sub-study (200 will receive the standard of care and 200 will be offered PoC syphilis testing in addition to the standard of care)

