The sample size of 500 participants was determined to have sufficient power to detect a difference in rates of vertical transmission of CT and NG based on 1) the prevalence of CT and/or NG among pregnant women in Botswana (10%),(5) and 2) the risk for vertical transmission of CT/NG to newborn infants during parturition (50%).(49-52). Antenatal CT/NG testing and treatment is expected to reduce vertical transmission by over 85%, from 5% in the control to 0.7% in the intervention group.(49, 50) When accounting for a 7% loss to follow-up rate, 250 women per arm will yield N=232 evaluable subjects. With N=232 evaluable samples per arm, we achieve 80.7% power to detect a 4.3% absolute difference in our primary endpoint, which is the proportion of vertical transmission of CT/NG, between the two groups, using a one-sided Fisher's Exact test, at a 0.05 significance level.

Methods for minimizing bias

Enrollment statistics, including total number of women attending their first antenatal clinic visit, total enrolled, total ineligible, and total who declined to participate, will be recorded in a weekly tally sheet and presented at bimonthly study meetings. Participant characteristics, such as sociodemographic characteristics, gestational age, HIV infection status, syphilis test results, obstetric history (e.g. history of preterm birth), in the testing and standard-of-care clinics will be monitored and compared to assess balance. Attrition will also be monitored and attrition bias will be assessed on a monthly basis.

Data Management

Data will be collected and managed using REDCap electronic data capture tools hosted at the Botswana Harvard AIDS Institute Partnership (BHP). REDCap (Research Electronic Data Capture) is a secure, web-based software platform designed to support data capture for research studies, providing 1) an intuitive interface for validated data capture; 2) audit trails for tracking data manipulation and export procedures; 3) automated export procedures for seamless data downloads to common statistical packages; and 4) procedures for data integration and interoperability with external sources.

Data will be entered offline at study clinics into CRFs on the REDCap mobile application on study tablets. At the end of each working day, data will be checked for any errors, discrepancies and missing data

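### Whether PoC syphilis testing works differently in women living with HIV is to be read from stratified models, with no estimate or test of the difference between strata

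*Protocol*

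**What the plan says.** The Aim 4 analysis is in Protocol section 3 (Study Design, Specific Aim 4, Analysis). "DiD will be performed using a logistic regression model", with an indicator for the PoC clinic, an indicator for the post period, "an interaction variable for the product of those two variables, and covariates". The outcome is "the proportion of eligible women who are tested for syphilis at their first ANC visit". The only product term is Post × PoC.

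The question about HIV is handled in one sentence: "Models will also be stratified by HIV status to see if PoC had a differential impact among WLH". The protocol gives no product term with HIV, no heterogeneity test and no rule for comparing the strata. The SAP contains no Aim 4 analysis, so nothing there fills the gap.

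The pre-test data "will include all 100 women enrolled in the standard of care clinic and all 100 women enrolled in the PoC testing clinic". For the post-test groups, section 5a says "200 will receive the standard of care and 200 will be offered PoC syphilis testing in addition to the standard of care". HIV status also decides which device is used in the PoC clinic: "women living with HIV will be offered a PoC syphilis test", while women who are HIV-uninfected or undiagnosed are offered the dual HIV/syphilis test.

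**The concern.** The stated aim of the stratified models is to learn whether the PoC effect differs by HIV status. That is a question about one quantity, the DiD effect in WLH minus the DiD effect in the other women. Two separate fits give two effects, each with its own standard error and p-value. Unless the two are contrasted, nobody obtains the quantity asked for or its uncertainty.

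If readers fall back on which stratum reached significance, stratum size can decide the answer. With 20% WLH (an assumption), the WLH model rests on about 20, 40, 20 and 40 women in the four clinic-by-period cells. It can miss an effect that the larger stratum detects. Because the HIV group determines the test offered, an apparent effect in one group only would be read as a statement about a device as well as about WLH, in a study meant to inform policy makers.

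**Working it through.** **Inputs from the documents.** Cells of 100 (standard pre), 200 (standard post), 100 (PoC pre) and 200 (PoC post); binary outcome; logistic DiD. The documents give no power or subgroup figure for Aim 4, so there is nothing to reproduce. The only stated alpha, "at a 0.05 significance level" in the SAP's Sample size section, is one-sided and belongs to the CT/NG endpoint.

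**Assumptions.** Two-sided 0.05; WLH share 15–30%; baseline testing 60–80%, with 90–95% also examined; the same true DiD odds ratio (OR) in both strata, from 1 to about 6; no covariates.

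**Step 1: standard error.** For a stratum with share f, SE = √Σ[1/(f·n·p(1−p))] over the four cells. Take baseline 70% and OR 3. The odds go from 0.7/0.3 = 2.333 to 7, so the PoC post rate is 7/8 = 87.5%. Then p(1−p) is 0.21 in three cells and 0.1094 in the fourth.
- WLH, f = 0.2: 0.2381 + 0.1190 + 0.2381 + 0.2286 = 0.8238; SE = 0.908.
- Others, f = 0.8: 0.8238/4 = 0.2060; SE = 0.454.
- All women: 0.8238/5 = 0.1648; SE = 0.406.

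**Step 2: power.** With ln 3 = 1.0986, power is about Φ(1.0986/SE − 1.960): 23% in WLH, 68% in the others, 77% overall.

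**Step 3: chance that exactly one stratum is significant.** 0.228 × (1 − 0.678) + 0.678 × (1 − 0.228) = 0.073 + 0.523 = 0.60. Simulation (20,000 replicates) gives 60.5%.

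**Step 4: the same over the grid** (baseline 60–80%, WLH 15–30%, Wald):

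| Common DiD OR | Exactly one stratum significant |
|---|---|
| 1 | about 10% |
| 1.5 | 18–23% |
| 2 | 31–44% |
| 3 | 49–66% |
| 4 | 49–68% |
| 6 | 32–68% |

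The 32% arises at OR 6, baseline 60% and 30% WLH, where the WLH stratum itself has 69% power.

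**Step 5: simulated logistic DiD** (40,000 replicates, 0.5 correction for empty cells):
- 75% to 95%, OR (0.95/0.05)/(0.75/0.25) = 6.33: about 74%, 63% and 47% at 15%, 20% and 30% WLH. At 20% WLH, 61 of the 63 points are significance in the other women only.
- 75% to 86%, OR about 2: about 35%.
- 90% to 95% and 95% to 98%: 11–21% across the two.

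Over all simulated scenarios the range is 5% (no effect, 90% baseline) to 83% (80% baseline, OR 6, 15% WLH).

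**Step 6: direct test of the difference.** With identical effects it rejects in 0.5–5.6% of simulated studies. Its SE in the Step 1 example is √(0.8238 + 0.2060) = 1.015, which is 2.5 times that of the overall DiD term. The ratio of the two DiD odds ratios detectable with 80% power is exp[(1.960 + 0.842) × 1.015] ≈ 17. It is about 24 at 15% WLH and 12 at 30%.

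**Step 7: sparse cells.** In the 75% to 95% case, 5–24% of simulated WLH strata have a cell in which all or none are tested. At 90% baseline, 9–77% of simulated studies have such a cell somewhere.

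**The case against.** The best defence is that the protocol never says significance will be compared across strata. Each stratified model also yields an estimate and a standard error. The strata contain different women, so the difference and its interval could be computed from them. This is correct, and it defines the point: the comparison is left unspecified, and no faulty decision rule is written down. A reader might infer that the plan will judge by stratum p-values; the text does not support that.

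A reader might also infer that identical effects will usually produce discordant significance. That is not supported either. The proportion exceeds one half mainly at odds ratios of about 3 or more with a small WLH stratum. It stays below one half at an odds ratio of 2 or less, and it is low when baseline testing is very high. Routine syphilis testing is already standard care at the first visit, so a high baseline with a small gain is plausible. Often is the most that can be said.

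It can further be argued that the direct test has so little power that it adds nothing, and that a non-significant result would invite the opposite error. The power limit stands. It is a reason to report the difference with its wide interval and label it exploratory; it does not justify leaving the difference out. Finally, this is a secondary question within a sub-study, and neither the Aim 4 primary DiD nor the CT/NG endpoint is affected. That limits the weight of the point.

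**Conclusion.** The point holds in limited form. The plan states a purpose, detecting a differential impact among WLH, and names only stratified models to serve it. It provides no estimate, interval or test for the difference between the two DiD effects.

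If the strata are compared by significance, an identical effect appears in exactly one stratum in about 10–20% of studies for small effects or a very high baseline, about 35% at an odds ratio of 2, and mostly about 47–74% at odds ratios of 3 to 6. It is lower than that in some combinations, such as the 32% in Step 4. A direct test gives about 1–5%. These figures rest on an assumed WLH share of 15–30%, assumed baselines and effects, two-sided 0.05 and an unadjusted model. The documents supply none of these for Aim 4.

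Even a correct interaction would not show that HIV status itself changes the effect, because the type of PoC test offered changes with it.

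**What to change.** Replace the stratification sentence with a direct contrast:

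- Fit one logistic model with PoC, Post, HIV, all three two-way products and PoC × Post × HIV. Compared with the planned model this adds HIV, HIV × PoC, HIV × Post and the three-way term. Contrasting the two independent stratum estimates is equivalent if there are no covariates or if every covariate also interacts with HIV.
- Report the difference between the two DiD effects (the ratio of odds ratios) with its 95% CI as the answer on differential impact. Keep stratum estimates as description.
- Label the analysis exploratory, and state that a non-significant interaction is not evidence of no difference.
- Name in advance a penalised or exact method for use if a cell is all tested or none tested.
- State that HIV status and type of PoC test cannot be separated.

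The cost is one model and a few sentences. HIV status is already to be abstracted for all participants under Aim 4 Data collection, so no new data are needed.
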